1. BACKGROUND

1.1 Introduction

Inflammation in the body is increasingly being identified as one of the factors that contribute to the exacerbation or the onset of diseases, especially in regards to today's context of metabolic diseases like cardiovascular diseases and type II diabetes. Inflammation occurs as part of the body's normal response to damaged surrounding tissues and cells which, if persistent, may turn chronic and result in illness (Weiss, 2008). Inflammation is usually tackled by the immune system, where the various types of white blood cells and other immune cells will deliver signals to fight and alleviate the damage.

Beer is an alcohol-containing beverage that is one of the culturally oldest beverages in the world (Preedy, 2009). It is considered a social drink that is widely consumed. While the excessive consumption of alcohol is widely known to be correlated negatively with health, there have been increasing evidences showing that moderate alcohol consumption has a beneficial impact on health, in particular towards immunity and research has proven that it is a potent immunomodulator (Szabo & Mandrekar, 2009).

The emerging field of microbiome has also shown that probiotics have a positive effect on gut health. Probiotics exhibit a therapeutic effect on immune responses, and even more so since 70% of our immune system lies in our gut (Vighi et al., 2008). Probiotics supplementation has also been identified as one of the ways to support our gut health.

These immune responses that the moderate consumption of alcohol and probiotics each demonstrated are geared towards an anti-inflammatory immune response which is associated with a better prognosis of inflammation in the body (Romeo et al., 2007). The combination of a probiotic strain with moderate beer consumption is thus expected/hypothesized to improve immunological outcomes towards an enhanced anti-inflammatory effect and enhanced gut health.

2. STUDY RATIONALE

2.1. Rationale for Study

Studies have shown that moderate alcohol consumption and probiotics have each shown immunomodulatory anti-inflammatory effects. However, to our knowledge, the effect of adding a probiotic strain to a beer drink, together with moderate alcohol consumption, on immunity and gut microbiome has yet to be studied. The probiotic beer used in this study taps on this unexplored research area and may potentially serve as a more healthful option to consumers than normal beer in the future, given the vast popularity of this beverage and probiotics.

2.2. Rationale for Test Foods

The beers used in this study will be normal beer and probiotic beer. Each beer can will have

3.5-5% alcohol, with a total volume of 330mL per can. The ingredients used in the beer are water, grains (Barke Pilsner, Floor-Malted Bohemian Wheat, Golden Naked Oats, and dextrin malt), raspberry puree, and yeast. Lactic acid bacteria (*Lactobacillus paracasei* Lpc-37®, or *Lactobacillus paracasei* LAFTI®L26) will be added for the probiotic beer.

Beer production took place at Brewerkz, a licensed manufacturer. The milled grains were mashed with brewing water and subsequently boiled to produce wort (unhopped, wheat-based). The wort was then inoculated with a probiotic strain and *Saccharomyces cerevisiae* yeast (SafAle S-04). After fermentation and cold crash, the yeast accumulated at the bottom of the fermentation tank was removed. The beer was then force-carbonated, packaged (in cans or kegs), and kept cold during storage. Probiotic cell count was determined to ensure that the final beer contains at least 1 billion colony-forming units (CFU) per serving at the time of consumption.

2.3. Rationale for Study Population

This study will recruit 30 Chinese healthy male participants. The outcome of interest is the change in immunological parameters to observe an improvement in anti-inflammatory effect, as well as any changes in gut microbiota.

2.4. Rationale for Study Design

A within-subject crossover study design is utilised to compare the immunological outcomes of moderate beer drinking and moderate probiotic beer consumption.

3. HYPOTHESIS AND OBJECTIVE

3.1. Hypothesis

The moderate consumption of probiotic beer is hypothesised to improve gut health and immunological parameters.

3.2. Objective

The objective of this research is to study the immunological and gut microbiome effects of moderate probiotic beer consumption.

4. POTENTIAL RISKS AND BENEFITS

4.1. Potential Risks

1. Minimal risk is anticipated. Some discomfort, pain, bleeding or bruising at the site of the needle stick may occur during collection of blood samples. There is a risk of vein collapse during the venepuncture procedure. In the case of such events, blood will be attempted to be drawn from a different vein.

2. The beers used in this study will be brewed and packaged by a licensed production company, Brewerkz. The ingredients of the beers will be made known to the subject before their participation in the study. In a rare unfortunate event, a food allergy is possible. In the case of a food allergy, the subject will be removed from the study and directed to receive proper medical treatment. Brewerkz is committed to ensure that there is no contamination in the beer production. All equipment used in the manufacturing of the beer undergoes cleaning with strong cleaning solution at high temperature and further sanitized with SFA approved acid solution (peroxyacetic acid, 8th schedule). The effectiveness of the cleaning and sanitation process is confirmed using an onsite test kit (ATP Luminometry) as an indicator for presence or absence of contaminants and cleanliness level. Before piping/ connectors are attached to inlet or outlet ports of tanks, the attachment surfaces are rinsed with sanitizer solution (Isopropyl alcohol) and immediately burned to disinfect the area.

4.2. Potential Benefits

Results from the study will be meaningful to the development of a more healthful alternative to normal beer. There will be no direct benefit to the subjects.

5. STUDY POPULATION

5.1. Sample size

The sample size for the present study was calculated with 90% power and a two-sided 0.05 significance level. At least 21 subjects would be needed for this study to find a significant increase in cytokine levels. Based on the 2007 study by Romeo et al. titled 'Changes in the Immune System after Moderate Beer Consumption', there was a significant increase in the cytokine IFNg in men comparing between a 30-day abstinence period and a 30-day moderate beer consumption period. From their data, the standard deviation of the difference between the two periods and the difference in their means was derived as 8287 pg/ml and 6208 pg/ml respectively. Using these values and a 90% power with 0.05 significance level, the minimum sample size was calculated to be 21. To account for a loss to follow-up, 30 subjects will be recruited for this study.

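### The 90% power with 21 subjects is calculated for beer versus abstinence and is unsupported for the probiotic-versus-normal-beer comparison that the crossover makes

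*Combined protocol and SAP*

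**What the plan says.** Section 5.1 (Sample size) states: "At least 21 subjects would be needed for this study to find a significant increase in cytokine levels". It sets 90% power and a two-sided 0.05 level. Both inputs come from one published study in which IFN-gamma rose in men, "comparing between a 30-day abstinence period and a 30-day moderate beer consumption period". From that study, "the standard deviation of the difference between the two periods and the difference in their means was derived as 8287 pg/ml and 6208 pg/ml". The section concludes: "Using these values and a 90% power with 0.05 significance level, the minimum sample size was calculated to be 21". Recruitment is raised to 30 to allow for loss to follow-up, with no loss rate given.

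The trial itself is described differently:

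- Section 2.4 says the crossover is used "to compare the immunological outcomes of moderate beer drinking and moderate probiotic beer consumption".
- Section 6.1 gives two weeks on each beer with a one-week washout, and Section 6.2 randomises the order of the two beers. Alcohol is present in both arms.
- Section 7 derives changes from baseline in each arm, assigns differences between groups to a mixed model, and for secondary measurements also compares the two arms with a paired t-test.
- Section 2.1 says that the effect of adding a probiotic to beer "on immunity and gut microbiome has yet to be studied".

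**The concern.** The effect of drinking beer rather than no alcohol is not the effect of adding a probiotic to beer. In this crossover the alcohol is common to both arms, so the between-beer difference isolates the probiotic. An effect size and SD from beer versus abstinence carry no direct information about it.

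Section 5.1 is the plan's only statement of what the trial can detect and the only basis for its size. A reader is likely to take it as 90% power to detect a probiotic effect, and could then read a non-significant between-beer result as evidence that the probiotic does nothing. The documents do not support that inference.

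**Working it through.** **Inputs (Section 5.1).** Mean difference 6208 pg/ml; SD of the paired difference 8287 pg/ml; two-sided alpha 0.05; power 90%; 21 subjects required, 30 recruited.

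**Step 1: reproduce the plan's figure.** Standardised effect d = 6208/8287 = 0.749. For a paired t-test, power comes from the noncentral t distribution with n−1 degrees of freedom and noncentrality d√n.

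- n=20: 88.8%
- n=21: 90.4%
- n=30: 97.7%

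The smallest n reaching 90% is 21, which matches the plan.

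**Step 2: compare the two contrasts.**

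| | Source of the inputs | This trial |
|---|---|---|
| Conditions | Beer versus abstinence | Probiotic beer versus normal beer |
| Length of each period | 30 days | 14 days |
| Alcohol | One condition only | Both conditions |
| Effect and SD for the contrast | 6208 and 8287 pg/ml | None given |

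**Step 3: what can be said without borrowed inputs.** Solving the same power function for d at 90% gives a detectable difference, in units of the SD of the within-subject between-beer difference, of

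- 0.744 SD with 21 completers
- 0.612 SD with 30 completers

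If the differences are analysed with a period term (n−2 degrees of freedom), these become 0.747 (sequences of 11 and 10) and 0.613 (15 and 15), so the choice hardly matters when sequence sizes are balanced.

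**Step 4: the SD needed to keep 90%.** The largest SD of the between-beer difference that preserves 90% power is the assumed effect divided by the detectable d (unrounded).

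| Assumed probiotic effect | 21 completers | 30 completers |
|---|---|---|
| 6208 pg/ml (all of the beer effect) | 6208/0.744 = 8345 | 6208/0.612 = 10,136 |
| 3104 pg/ml (half) | 3104/0.744 = 4172 | 3104/0.612 = 5068 |

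**Step 5: illustrations under assumed SDs.** Neither SD below is given in the documents for the between-beer contrast.

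*Illustration 1: SD of the between-beer difference = 8287.* The detectable difference is 0.744 × 8287 = 6165 pg/ml with 21 (99% of 6208) and 0.612 × 8287 = 5075 with 30 (82%).

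*Illustration 2: 8287 is the SD of each arm's change and the two changes are uncorrelated.* The SD of the difference is then 8287 × √2 = 11,720.

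| | Power, n=21 | Power, n=30 |
|---|---|---|
| SD 8287, effect 6208 | 90% | 98% |
| SD 8287, effect 3104 | 37% | 51% |
| SD 11,720, effect 6208 | 64% | 80% |
| SD 11,720, effect 3104 | 21% | 29% |

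An SD below 8287 would give higher power than Illustration 1.

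**The case against.** The strongest reply is that Section 5.1 never mentions a between-beer difference. It speaks of an increase in cytokine levels and says openly where its inputs come from. The hypothesis, "The moderate consumption of probiotic beer is hypothesised to improve gut health and immunological parameters", and the objective, "to study the immunological and gut microbiome effects of moderate probiotic beer consumption", are not comparative. Section 7 takes change from baseline in each arm, and Section 6.3 requires a week without alcohol before the study starts. On that reading the powered quantity is a within-arm change, which is closer to beer versus abstinence.

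This reading is possible, and it is true that Section 5.1 does not say which contrast it powers. It does not rescue the 90%. The exposure is still 14 days rather than 30, and a within-arm change cannot separate the probiotic from the beer. If it were the target, the randomised comparison would have no power statement at all.

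It can also be said that, with no prior data on the combination, borrowing the nearest available figures is understandable. That is fair. The fault lies in presenting the result as the power of this study without the caveat.

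Two further points stand in part. The effect fractions and the √2 factor are assumptions, so the illustrations show sensitivity and do not estimate the trial's power. And nothing in the plan proposes to treat a non-significant result as proof of no effect; the risk lies in how the 90% would be read.

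**Conclusion.** The concern holds. The calculation is numerically correct for beer versus abstinence, but nothing in the documents supports 90% power for probiotic versus normal beer. True power for that comparison is unknown. It could exceed 90% if the SD is small, or fall well below it if the probiotic effect is only a fraction of the effect of beer itself.

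Only the detectable differences in SD units (0.74 with 21 completers, 0.61 with 30) are free of assumptions about the effect and its SD; they rest on the paired t-test with its usual normality assumption. Every pg/ml and power figure for the between-beer contrast depends on an assumed SD.

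This should be fixed. The design remains usable, but its stated justification does not match its randomised comparison.

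**What to change.** In Section 5.1:

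1. State that the 6208/8287 calculation applies to beer versus abstinence, and remove the implication that 21 subjects give 90% power for this study's comparison.
2. Name the contrast as probiotic minus normal beer, and name the outcome it refers to. IFN-gamma is the one used in the calculation, but Section 7 lists C-reactive protein, white cell count and cytokine panels without singling it out.
3. Give the detectable difference at 90% power, two-sided 0.05, paired t-test: 0.74 SD of the within-subject difference with 21 completers and 0.61 SD with 30. Label any translation into pg/ml as resting on an assumed SD.
4. Add that a non-significant between-beer result does not exclude smaller probiotic effects.

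Keep n=30. The cost is protocol wording and a less favourable power statement; no participants are added, and visits and analysis are unchanged.

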5.2. Recruitment procedure

Recruitment of subjects will be made through advertisement (i.e. posters) and word of mouth. Potential subjects will be contacted and screened for eligibility according to the inclusion and exclusion criteria by the research personnel. The research personnel will identify eligible candidates and will explain the study rationale, procedures, and potential risks and benefits as stated in the study protocol. The Participant Information Sheet (PIS) will be provided for the candidates to read prior to their decision to participate in the study. The candidates will be encouraged to ask questions about the study and have adequate time to make a decision. Informed consent will be acquired from eligible candidates before enrolment into the study. Subsequent visits and any other administrative details will be arranged between the research personnel and participants.

5.3. Inclusion criteria

Subjects must meet all of the inclusion criteria to participate in this study:

1. Ability to give informed consent.
2. 21 – 60 years of age (inclusive) at screening.
3. Healthy male, as determined by medical history, physical examination and laboratory results within normal reference range for the population or investigator site, or results with acceptable deviations that are judged to be not clinically significant by the investigator.
4. Race must be Chinese.
5. Willing to consume 1 beer can per day for 14 days.
6. Not on any regular medications (western/ traditional).
7. No family history of alcoholism.

5.4. Exclusion criteria

1. Female.
2. A current smoker, have smoked, or is a user of tobacco products for the past 2 years.
3. History or presence of current lipid and cardiovascular disorders, respiratory, hepatic, renal, gastrointestinal, endocrine, lipid disorder, haematological, malignancy or neurological disorders capable of significantly altering the performance of the biomarker panel; or of interfering with the interpretation of data.
4. History of alcoholism, alcohol dependence, alcohol abuse, alcohol allergy and/or any other alcohol use disorders.
5. History of Type 1/ Type 2 diabetes and use of anti-diabetic medications in the past.
6. Regular use of medication that are known to have an effect on immune function.
7. Regular use of aspirin.
8. A naïve alcohol drinker.
9. Persons with known or ongoing psychiatric disorders or drug abuse within 3 years.
10. Active infection requiring systemic antiviral or antimicrobial therapy that will not be completed prior to first visit of the study.
11. Treatment with any investigational drug, or biological agent within one (1) month of screening or plans to enter into an investigational drug/ biological agent study during the duration of this study.
12. Significant change in weight (+/- 5%) during the past month.
13. Antibiotic use in the past 2 months.

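### Section 4.1 names food allergy to the study beers as a risk, but the only allergy in the eligibility criteria is to alcohol, so a man with a known allergy to a listed ingredient can meet every written criterion

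*Combined protocol and SAP*

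**What the plan says.** **Hazard.** Section 4.1 states: "In a rare unfortunate event, a food allergy is possible".

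**Handling of the hazard.** Section 4.1 gives one measure before exposure, "The ingredients of the beers will be made known to the subject before their participation in the study", and one after a reaction, "In the case of a food allergy, the subject will be removed from the study and directed to receive proper medical treatment".

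**Product.** Section 2.2 states: "The ingredients used in the beer are water, grains (Barke Pilsner, Floor-Malted Bohemian Wheat, Golden Naked Oats, and dextrin malt), raspberry puree, and yeast". The same section says that lactic acid bacteria "will be added for the probiotic beer".

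**Eligibility.** Exclusion 4 in section 5.4 reads "History of alcoholism, alcohol dependence, alcohol abuse, alcohol allergy and/or any other alcohol use disorders". No other criterion in 5.3 or 5.4 mentions allergy. The nearest general ones are inclusion 3, "Healthy male, as determined by medical history, physical examination and laboratory results within normal reference range", and inclusion 5, "Willing to consume 1 beer can per day for 14 days".

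**Supply.** Under section 6.4, cans are handed over at Visits 2 and 4, one to be drunk each evening for 14 days.

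**The concern.** The plan recognises a hazard of its own product and treats allergy as a matter for eligibility, but writes the criterion for alcohol alone. The ingredients that could cause the food allergy named in 4.1 are not covered. Staff who apply 5.3 and 5.4 as written have no item that makes them ask about, or act on, a known allergy to wheat, oats, malt, raspberry, yeast or the added bacteria.

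What is at stake is an avoidable reaction in a healthy volunteer, for whom section 4.2 promises no direct benefit. The risk can be reduced cheaply before the first can is supplied.

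**Working it through.** The plan gives no figure on this point, so the check is to set its sections side by side.

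**1. Is the hazard acknowledged?** Yes, in 4.1, as possible but rare.

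**2. Are the possible sources identified?** Yes, in 2.2: wheat, oats, malt, raspberry and yeast in the beer, and lactic acid bacteria in the probiotic beer.

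**3. Does any criterion cover an allergy to these sources?** The 7 + 13 = 20 criteria contain one allergy term, for alcohol. The criteria that come closest are:

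| Criterion | Does it require exclusion for a known ingredient allergy? |
|---|---|
| Inclusion 3 (healthy by history, examination and laboratory results) | No. It allows judgement but does not name allergy, and a man who simply avoids one food may reasonably be called healthy. |
| Inclusion 5 (willing to drink the beer) | No. It records the candidate's own decision. |
| Inclusion 6 (no regular medication) | No. A food allergy need not involve regular medication. |
| Exclusion 3 (listed organ-system disorders) | No. Allergic and immune disorders are not listed. The qualifier concerns the biomarker panel and interpretation of the data, not product safety. Some ingredient-related gastrointestinal disease might be caught. |
| Exclusion 4 | Alcohol only. |

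**4. Does the screening procedure fill the gap?** Section 5.2 has staff screen candidates against the inclusion and exclusion criteria. At Visit 1 (section 6.4), staff go through those criteria, and the detailed explanation follows once eligibility is confirmed. The written list therefore decides eligibility, and no separate allergy question is described.

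**5. When do the 4.1 measures act?** Disclosure comes before participation but relies on the candidate to make the connection. Removal comes after a reaction.

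**6. Exposure.** 2 periods × 14 days × 1 can = 28 cans per man. This is exposure, not a measure of risk.

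**7. How many men?** The documents give no frequency of ingredient allergy. As an assumption only, let a proportion p of otherwise eligible men have one. The chance of at least one among 30 is 1 − (1 − p)^30:

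- p = 0.5%: 1 − 0.995^30 = 0.140, about 14%
- p = 5%: 1 − 0.95^30 = 0.785, about 79%

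The range is too wide to serve as an estimate. It ignores men who decline once told the ingredients, and it counts men with an allergy, not reactions.

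**The case against.** The strongest reply is that 4.1 and 5.4 do not contradict each other. Section 4.1 describes a residual risk and the response to it, and candidates are adults who learn the ingredients before taking part. Section 5.2 adds an explanation of risks, an information sheet, the chance to ask questions and time to decide. A man who knows of a wheat or raspberry allergy would probably decline, or would fail the willingness criterion, and an investigator taking a history could turn him away under inclusion 3. The consent pages, the information sheet and the data collection sheet are also not available here, so a question about allergy may exist in one of them.

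Much of this stands. It lowers the risk, and it limits the finding to what the criteria say. It does not supply a required check: disclosure and willingness depend on the candidate, and inclusion 3 leaves the matter to discretion. A question on another form would help, but it would not be an eligibility criterion.

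A reader might infer more than the text supports:

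- **That an allergic man is bound to qualify, or that the cans are drunk at home unobserved.** The first overlooks inclusions 3 and 5. The second is an inference from a 14-day supply and evening use; the plan does not state the place.
- **That sensitivity to the beer distorts the inflammatory markers.** The documents offer no evidence of this. The base is common to both beers, so an effect of it would largely cancel in the within-man comparison. Only the bacteria differ, and no effect of an allergy to them on the markers is documented. A criterion on known allergy would in any case not remove subclinical sensitivity.
- **That the size of the gap can be read from the share of ingredients covered, or from the 30 − 21 = 9 spare places.** Neither measures risk. Alcohol is not in the 2.2 ingredient list, so no such share can be formed, and losing one of 30 men matters little.
- **That intolerance to alcohol should be excluded too.** Nothing in the documents argues for it.

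**Conclusion.** The point holds as a gap in participant safety. The plan names food allergy as a risk and lists the ingredients, yet its only allergy criterion concerns alcohol. A man with a known ingredient allergy can meet every written criterion, and the safeguards that exist reduce the risk without requiring anyone to check.

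Its size in patients cannot be derived from the documents. The plan itself calls the event rare, and disclosure gives partial protection. The reason to act is that prevention is almost free, not that many men are expected to be affected. The conclusion rests on the wording of 5.3, 5.4 and Visit 1, and it assumes nothing about forms outside the documents. It has no bearing on the randomisation, the sample size of 21 or the analysis in section 7.

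**What to change.** Reconcile section 5.4 with sections 4.1 and 2.2, so that eligibility also covers known allergy to any listed ingredient of the study beers, including the lactic acid bacteria added to the probiotic beer. Put the question at Visit 1, before any cans are supplied, and record the answer with the other eligibility checks. The exact wording is for the investigators.

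The cost is one line in 5.4, one screening question and possibly the loss of a few candidates, a number that the documents do not allow one to estimate.
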